A non-invasive intervention (BreESTim) for management of phantom limb pain (PLP) after limb amputation

NCT04750525

Version Date:12/03/2020

A non-invasive intervention (BreESTim) for management of phantom limb pain (PLP) after limb amputation

Protocol (CPHS HSC-MS-20-1032)

1. Protocol Title: A non-invasive intervention (BreESTim) for management of phantom limb pain (PLP) after limb amputation

PI: [name], PhD

Co-Investigators: [name]; [name], MS

Study Coordinator: not identified

Population: amputee subjects

Number of Sites: single site

Study Duration: planned for 3 years

Subject Duration: estimated 64 subjects

2. Specific aims and research questions:

The overall goal of this project is to compare the effectiveness of innovative intervention of breathing-controlled electrical stimulation (BreESTim) and conventional electrical stimulation (ESTim) in management of neuropathic phantom limb pain in patients after limb amputation.

3. Background/literature review, Justification and Significance:

a) Importance of the problem

1) The need and target population

In the United States, there are approximately 1.7 million people living with limb loss(Ziegler-Graham et al. 2008). It is estimated that one out of every 200 people in the U.S. has had an amputation(Adams et al. 1999). Limb amputation could lead to three non-exclusive phenomena, including phantom limb pain (painful sensation from the absent limb, i.e., phantom limb), phantom limb sensation (any sensation in the absent limb, except pain), and stump pain (pain localized in the residual limb) (Nikolajsen and Jensen 2001). Phantom limb pain (PLP) is a complex condition that is caused by peripheral nerve damage from amputation. Similar to neuropathic pain from other etiologies (e.g., spinal cord injury), PLP is characterized by spontaneous and ongoing pain, described as burning, shooting, prickling or electrical, and/or pain in response to innocuous stimuli (allodynia) and exaggerated pain in response to noxious stimuli (hyperalgesia) (Bennett 2010). PLP has increasingly been recognized as an important contributor to suffering, poor rehabilitation outcomes, reduced quality of life, and employment status of the persons with PLP after amputation. This is because of the following facts.

- PLP is very common(Werhagen et al. 2004). About 60-80% amputees have PLP at 2 years post-amputation (Jensen et al. 1985; Ephraim et al. 2005).

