limbs (Fig 1B), suggesting central sensitization in patients with PLP. In contrast, electrical sensation threshold (EST) was increased on the affected limb as compared to the sound limb within the PLP group, but there were no significant differences in EST between the PLP and non-PLP group. There was essentially no significant difference in other thresholds (thermal and tactile).

- **Non-pharmaceutical modalities (acupuncture, TENS, aversive electrical stimulation) for PLP management**

Electrical stimulation (TENS) for pain Various neurostimulation techniques, including transcutaneous electrical nerve stimulation (TENS) (Norbrink Budh and Lundeberg 2004), spinal cord stimulation (Finnerup et al. 2001b), deep brain stimulation (Murphy and Reid 2001), and transcranial direct current stimulation (Fregni et al. 2006) have been used for management of neuropathic pain. We are particularly interested in non-invasive stimulation that is relevant to our study – TENS.

TENS is noninvasive, inexpensive, safe and easy to use. TENS for pain relief was fully accepted by the medical field after the publication by Wall and Sweet in 1967 (Wall and Sweet 1967) which provided experimental evidence supporting the gate theory of pain (Melzack and Wall 1965). TENS is usually applied at varying frequencies, intensities and pulse duration of stimulation for a prescribed treatment time. Frequency of stimulation is broadly classified as high frequency (>50Hz) or low frequency (<10Hz) or bursts of high frequency stimulation at a much lower frequency. Intensity is determined by patient's response as either at the sensory level or motor level TENS. With the sensory level TENS, the stimulation intensity (voltage, or amplitude) is increased until the patient feels a comfortable tingling/tapping sensation without muscle contraction (twitching). With the motor level TENS, the intensity is increased to produce a motor contraction, but electrical stimulation is not noxious or painful. The usual TENS settings are high-frequency and low-intensity, or low-frequency and high-intensity. TENS has been applied to a variety of pain conditions, including phantom limb pain. Overall, the clinical effectiveness of TENS is controversial (see Review(Sluka and Walsh 2003; Mulvey et al. 2010; Johnson and Bjordal 2011)).

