In these two cases, BreESTim to acupoints on the forearm was not likely to modify the sources of noxious stimuli at the level of spinal cord injury (thoracic area) or at the residual limb (i.e., lower extremity). Rather, BreESTim modified how patients react to the noxious stimuli at the central level, i.e., the affective response to the same stimuli. Our case reports suggest that patients could tolerate the same noxious stimuli better after BreESTim. This is possibly realized by increasing pain threshold as a final result from the intervention, i.e., de-sensitization, or less sensitive to painful stimuli.

[figure not shown]
Figure 2 *Change of electrical pain threshold as percentage of pre-intervention values after BreESTim and EStim in healthy subjects. Standard errors are presented (From Li et al. 2013(Li et al. 2013))*

NOTE: *The intensity of electrical stimulation was comparable between BreESTim and EStim, suggesting that the effect is not mainly mediated by electrical stimulation itself.*

To test the hypothesis that BreESTim modifies pain threshold, subsequently resulting in reduction of neuropathic pain, we recently compared pain thresholds before and after BreESTim and EStim (Li et al. 2013). Two interventions were tested in the same healthy subjects in a randomized order, but at least 3 days apart in order to exclude any possible carry-over effect from the previous intervention. The results showed that BreESTim significantly increased electrical pain threshold, while EStim significantly decreased electrical threshold. Other thresholds (thermal, electrical sensation, and tactile sensation) remained the same after both interventions. Collectively, these findings suggest that BreESTim has selectively modified electrical pain threshold, i.e., affective component.

Figure 3. Changes of electrical pain threshold as percentage of pre-intervention values after BreESTim and Breathing-only. Standard errors are shown.

To further examine whether BreESTim-induced analgesic effect is primarily caused by voluntary breathing, we compared the effect of BreESTim and Breathing-only on experimentally induced pain in healthy subjects in another study in 2015(Hu et al. 2015). The same protocol was used. Electrical pain threshold increased to a similar extent as previously reported after BreESTim, but there was almost no change after Breathing-only (Figure 3).

- **BreESTim integrates multiple pain coping mechanisms**

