In the BreESTim treatment, a single-pulse electrical stimulus is delivered to the nerve when patients are taking fast, strong, and deep inhalation, similar to a deep breath but faster and stronger. Voluntary inhalation plays an important role in this intervention. Voluntary inhalation is defined as effortful deep and fast inhalation. Subjects are instructed to take a deep breath, similar to routine deep breaths, but faster and stronger, usually involving obvious expansion of chest wall. It has been reported that there are respiratory specific connections between the insula and the activity of pulmonary stretch receptors (Gaytan and Pasaro 1998; Hanamori et al. 1998). Experimentally, the airflow rate is monitored online. When the airflow rate reaches 40% of its peak, an electrical pulse is triggered (Li et al. 2012a; Li 2013). The frequency of BreESTim generally varies. As in our previous series of BreESTim experiments, subjects are usually comfortable to continue voluntary breathing for 20 – 30 electrical stimuli without a break. As seen in Figure 8, BreESTim is delivered at about every 2 seconds. The single-pulse electrical stimulus is a square wave with a width of 0.1 ms. The intensity is set where subjects feel painful but yet tolerable, equivalent to 7 on the 0-10 VAS scale. When wearing a face mask, subjects usually tolerate such breathing very well. No hyperventilation has been reported (Li et al. 2012a; Li 2013).

In the EStim condition, subjects will also wear the face mask as in the BreESTim condition. The main difference is that subjects will be breathing automatically and comfortably and electrical stimulation pulses will be delivered randomly. The pulses will be programmed to randomly deliver at about every 2 seconds (between 1.9 seconds and 2.1 seconds). The pulse width will be the same at 0.1ms. Similarly, subjects control the intensity of electrical stimulation. For both BreESTim and EStim, they are strongly encouraged to increase the intensity to be painful yet tolerable gradually from their pain threshold. The level of pain with painful stimulation will be 7 on the 0-10 VAS scale. The purpose is to make the intensity of electrical stimulation comparable between two conditions. According to previous studies, the intensity is comparable between BreESTim and EStim(Li et al. 2013; Li et al. 2014).The intensity of electrical stimulation will be recorded during the course of treatment.

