Inclusion criteria: A patient who 1) has neuropathic PLP after amputation of one limb, upper or lower limb; NOTE that BreESTim has been shown to be effective for neuropathic pain management in patients after traumatic and non-traumatic spinal cord injury in recent studies(Li et al. 2016; Li et al. 2018). Therefore, we plan to recruit patients with chronic neuropathic PLP from both traumatic and non-traumatic limb amputation. 2) has chronic pain, >3 months; 3) is between 18 to 75 years of age; 4) is stable on oral pain medications at least two weeks. Patients are instructed to continue their pain medications as prescribed during the intervention period.

Exclusion criteria: Patients will be excluded if they 1) are currently adjusting oral pain medications for their neuropathic pain; 2) have pain, but not neuropathic, e.g., from inflammation at the incision wound of the residual limb; 3) have a pacemaker to avoid possible side effect of electrical stimulation; 4) have amputation in multiple limbs; 5) are not able to follow commands, or to give consent; 6) have asthma or other pulmonary disease; 7) are not medically stable.

Gender will be balanced

Potential subject populations and recruitment: Subjects will be recruited from TIRR outpatient clinic.

6. Data Collection and Analysis

Data collection details have been described above. Data analysis is described here.

Experiment 1 Repeated-measures two-way ANOVA tests with factors INTERVENTION (2 levels, BreESTim and EStim) and TIME (pre- and post-intervention) will be tested on dependent variables, including VAS, QST thresholds (tactile, electrical, and thermal), to determine statistical significance between two interventions. Paired t-tests will be used to compare the duration of lasting hours between two interventions. p value is set at 0.05. As observed in the pilot data, we expect that BreESTim could have central desensitization and analgesic effects on patients with phantom limb pain, but no such effect after EStim. These findings would suggest that the central desensitization effect of BreESTim could be translated to analgesic effects in patients with PLP. Furthermore, the findings of analgesic effects along with desensitization effects in patients with PLP support central sensitization as a plausible mechanism that mediates post-traumatic PLP.

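### EStim is pain-matched stimulation without voluntary-breathing control, so the trial cannot show that BreESTim is superior to conventional electrical stimulation

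*Combined protocol and SAP*

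**What the plan says.** **The label.** Section 2 sets the goal as a comparison of "innovative intervention of breathing-controlled electrical stimulation (BreESTim) and conventional electrical stimulation (ESTim) in management of neuropathic phantom limb pain". Sections 3(a)1 and 3(a)3 repeat the word *conventional* and list what BreESTim is said to add over such stimulation. Section 3(a)2 expects the comparison to show superiority over the conventional technique, and section 3(a)3 foresees BreESTim joining routine care. Specific Aim 3 uses the same label, and section 4.D (Experimental Design) calls the comparator *regular*.

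**What conventional stimulation looks like.** Section 3(b)A singles out TENS as the "non-invasive stimulation that is relevant to our study". At sensory level the patient feels a comfortable tingle. At motor level, "With the motor level TENS, the intensity is increased to produce a motor contraction, but electrical stimulation is not noxious or painful". The text on aversive stimulation that follows treats painful intensity as a separate category.

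**What is delivered.** Section 4.D (Experimental setup) states: "For both BreESTim and EStim, they are strongly encouraged to increase the intensity to be painful yet tolerable gradually from their pain threshold". The target is a pain rating of 7 out of 10 in both conditions. For Experiment 3, the aversive quality is described as part of the treatment strategy.

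**Threshold data and planned reading.** For healthy subjects, the preliminary data section reports: "The results showed that BreESTim significantly increased electrical pain threshold, while EStim significantly decreased electrical threshold". The Main Research Hypothesis repeats the decrease after EStim. Section 6 plans an INTERVENTION by TIME analysis of variance for Experiment 1 and adds: "we expect that BreESTim could have central desensitization and analgesic effects on patients with phantom limb pain, but no such effect after EStim".

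**The concern.** The name of the comparator fixes what a positive result may claim. If BreESTim beats EStim, the protocol as worded would report superiority over conventional stimulation, a treatment that no subject receives. A clinician would read that as BreESTim against the TENS already in use. What was tested is whether painful pulses work better when tied to forceful voluntary inhalation than when delivered during quiet breathing.

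The second issue is narrower. Patients have no sham, no-treatment, conventional-TENS or breathing-only arm. If the two arms differ in electrical pain threshold, nothing outside them shows which one moved. In healthy subjects EStim did move, in the unfavourable direction.

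**Working it through.** **Step 1. Label against delivery.**

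| Feature | Protocol's account of TENS (3(b)A) | EStim (4.D) |
|---|---|---|
| Intensity | Comfortable, or motor contraction without pain | Painful, target 7 out of 10 |
| Rate | High (above 50 Hz) or low (below 10 Hz) | One pulse every 1.9 to 2.1 s |

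The EStim rate is 1/2.1 = 0.48 Hz to 1/1.9 = 0.53 Hz, which lies inside the low-frequency band. The departure is therefore the painful intensity, not the slow pulses.

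**Step 2. Are the advantages credited to BreESTim absent from EStim?** Sections 3(a)1 and 3(a)3 explain why BreESTim should beat conventional stimulation. Set against section 4.D:

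- Active patient involvement: subjects also control the intensity under EStim, so this is at least partly shared.
- Electroacupuncture effect: the same acupuncture points lie under the electrodes in both conditions, so this is shared.
- Habituation to aversive stimuli: both conditions aim at the same pain rating, so this is shared.
- Tolerance of higher intensity: the protocol aims to make intensity comparable between conditions, so the design tries to remove it.
- Voluntary deep, fast inhalation and pulses timed to it: BreESTim only.

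Pulse number is also matched: 120 per intervention in Experiment 1 and 240 per session in Experiment 3. The conventional stimulation of section 3(a) is thus not the EStim of section 4.D. The contrast isolates the last item, which combines breathing effort with pulse timing.

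**Step 3. How much of the trial is affected.** Experiments 1 and 3 compare BreESTim with EStim: 16 + 30 = 46 of 64 planned subjects. Experiment 2 (18 subjects) compares two BreESTim doses and is not affected.

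**Step 4. What the pilot shows (section 4.C, Experiment 1, three patients).**

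- Threshold after BreESTim: 29.3 − 22.8 = +6.5 mA. The protocol prints a 22.1% change. Dividing by the starting value gives 6.5/22.8 = 28.5%, and dividing by the end value gives 6.5/29.3 = 22.2%. Nothing here depends on which was used.
- Threshold after EStim: 23.6 − 23.4 = +0.2 mA, or 0.2/23.4 = 0.9%.
- Difference of changes: 6.5 − 0.2 = 6.3 mA. None of it comes from a fall after EStim.
- VAS: BreESTim 5.3 − 3.2 = 2.1 points lower; EStim 4.9 − 4.1 = 0.8 points lower; net 2.1 − 0.8 = 1.3 points.

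**Step 5. What the interaction can and cannot show.** Write the pre-to-post threshold changes as ΔB (BreESTim) and ΔE (EStim). With two interventions and two times, the interaction tests ΔB − ΔE and nothing else. A rise d after BreESTim with no change after EStim gives d − 0 = d. No change after BreESTim with a fall d after EStim gives 0 − (−d) = d. The TIME main effect averages the arms, (ΔB + ΔE)/2, so it does not estimate ΔB alone. Experiment 3 has three time levels, and the same ambiguity applies to each change from baseline.

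**The case against.** The design has a good defence. The protocol never says that EStim is TENS, and it lists low frequency with high intensity as a usual TENS setting. Matching pulse width, number, site and pain rating is the right way to ask what breathing-controlled delivery adds; a TENS arm would answer a different question. Superiority to conventional stimulation may not even be needed for clinical uptake, since the protocol names drugs as the standard of care and calls TENS effectiveness controversial. All of this stands. It supports keeping EStim as the comparator, but not the words *conventional* and *regular*.

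Three stronger readings are tempting, and the documents do not support them.

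- *EStim sensitises patients with phantom limb pain.* The threshold fall was in healthy subjects. In the three-patient pilot the threshold was essentially unchanged and VAS improved after EStim. Three patients cannot exclude a fall, but nothing shows EStim worsening pain, so the second point does not extend to VAS.
- *Section 6 would report desensitisation even if BreESTim did nothing.* Its inference starts from an expected pattern in which BreESTim has the effect and EStim does not, and Aim 1 also predicts a rise after BreESTim itself. What is missing is a written within-arm estimate and a rule for using it.
- *The comparison is invalid.* It is not. A difference against EStim bears directly on voluntary-breathing-controlled delivery.

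**Conclusion.** The concern holds as a limit on what may be claimed. In Experiments 1 and 3 the contrast is between BreESTim and painful stimulation of matched intensity without voluntary-breathing control. It cannot support superiority over conventional or regular stimulation, whatever its size or p value. The limit is one of scope, so no numerical bias is attached to it.

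For electrical pain threshold, the interaction alone does not identify which arm moved. The healthy-subject data make that ambiguity worth closing, while the pilot gives no sign that it operates in the target population.

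The conclusion assumes that EStim is delivered as section 4.D describes. Section 7 tells patients to raise the intensity to a level at which they feel comfortable, which does not agree with a target of 7 out of 10. Those passages must be reconciled, because they decide what the comparator is.

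**What to change.** 1. In section 2, sections 3(a)1 to 3(a)3, Specific Aim 3 and section 4.D (Experimental Design), replace *conventional* or *regular electrical stimulation*, where it names the comparator, with *intensity-matched painful electrical stimulation without voluntary-breathing control*. Saying only that the breathing trigger is removed would be incomplete, because effortful inhalation differs between arms too.
2. State once, in section 2, that superiority to conventional non-painful stimulation is not tested. Bring the superiority and routine-care statements in section 3(a) into line with this, and stop crediting BreESTim with features that EStim shares.
3. In section 6, Experiments 1 and 3, report each arm's pre-to-post change with a confidence interval beside the interaction. Attribute a threshold difference to BreESTim desensitisation only if the BreESTim arm's own threshold rises. This is a safeguard and not proof of efficacy, since expectation and regression to the mean can also move a single arm.

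The cost is a narrower permitted claim, some rewording and one extra estimate per arm for each outcome. It needs no new arm, patients or visits.

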A novel hypermnesia-hyperarousal model is proposed specifically to account for pain persistence and pain sensitization following a traumatizing event(Egloff et al. 2013). According to this model, a traumatizing event, such as limb amputation, usually results in activation of two self-protective mechanisms: hyper-sensitization (i.e., to detect a potential hazard as early as possible) and hypermnesia (i.e., not to forget the event in order to recognize it again and to avoid it). In case of severe traumatization like amputation, intense hypermnesia and hyperarousal are likely imprinted on the victim's memories, and result in pain chronification and lower pain detection and tolerance thresholds (i.e., sensitization). We are aware that chronic PLP is multi-factorial. This model, however, offers a plausible explanation for chronic pain that is "unexplained" by structural damages after amputation. For example, when associated with a negative emotional context, phantom limb pain could be perceived as aversive, and re-triggered by a stressful life event(Jensen et al. 1985). Furthermore, the concept of trauma-induced pain sensitization and chronification has also provided a theoretical framework for a potential novel intervention, such as the one proposed in this application.

Figure 1 Electrical sensation threshold (EST) (panel A) and electrical pain threshold (EPT) (panel B) in the PLP and non-PLP group. Mean and standard errors are shown.

In our recent study (Li et al. 2015), we examined sensory thresholds in patients after traumatic amputation. We found hypersensitization in amputees with chronic phantom limb pain, but not in amputees without phantom limb pain (Figure 1). Thus, the findings support the concept of pain sensitization and chronification as a plausible underlying mechanism for neuropathic phantom limb pain. Specifically, it was the first time that tactile, thermal and electrical thresholds were comprehensively compared between the residual limb and the contralateral sound limb in patients with and without phantom limb pain. As shown in Fig 1, electrical pain threshold (EPT) was only decreased in the sound limb in the phantom limb pain (PLP) group and no difference among other three

limbs (Fig 1B), suggesting central sensitization in patients with PLP. In contrast, electrical sensation threshold (EST) was increased on the affected limb as compared to the sound limb within the PLP group, but there were no significant differences in EST between the PLP and non-PLP group. There was essentially no significant difference in other thresholds (thermal and tactile).

- **Non-pharmaceutical modalities (acupuncture, TENS, aversive electrical stimulation) for PLP management**

Electrical stimulation (TENS) for pain Various neurostimulation techniques, including transcutaneous electrical nerve stimulation (TENS) (Norbrink Budh and Lundeberg 2004), spinal cord stimulation (Finnerup et al. 2001b), deep brain stimulation (Murphy and Reid 2001), and transcranial direct current stimulation (Fregni et al. 2006) have been used for management of neuropathic pain. We are particularly interested in non-invasive stimulation that is relevant to our study – TENS.

TENS is noninvasive, inexpensive, safe and easy to use. TENS for pain relief was fully accepted by the medical field after the publication by Wall and Sweet in 1967 (Wall and Sweet 1967) which provided experimental evidence supporting the gate theory of pain (Melzack and Wall 1965). TENS is usually applied at varying frequencies, intensities and pulse duration of stimulation for a prescribed treatment time. Frequency of stimulation is broadly classified as high frequency (>50Hz) or low frequency (<10Hz) or bursts of high frequency stimulation at a much lower frequency. Intensity is determined by patient's response as either at the sensory level or motor level TENS. With the sensory level TENS, the stimulation intensity (voltage, or amplitude) is increased until the patient feels a comfortable tingling/tapping sensation without muscle contraction (twitching). With the motor level TENS, the intensity is increased to produce a motor contraction, but electrical stimulation is not noxious or painful. The usual TENS settings are high-frequency and low-intensity, or low-frequency and high-intensity. TENS has been applied to a variety of pain conditions, including phantom limb pain. Overall, the clinical effectiveness of TENS is controversial (see Review(Sluka and Walsh 2003; Mulvey et al. 2010; Johnson and Bjordal 2011)).

Several mechanisms are used to support the use of TENS for pain relief. The most common one is the gate control theory (Melzack and Wall 1965). Briefly, according to the gate control theory, small diameter fibers excite cells in the spinal cord that sends information to a higher center for the perception of pain. Large diameter fiber input reduces noxious input of nociceptor by activation of inhibitory neurons in the substantia gelatinosa of the spinal cord. Accordingly, stimulation of large diameter fibers by TENS inhibits nociceptive fiber evoked responses in the dorsal horn (Melzack and Wall 1965). Another theory is that TENS increases the release of endogenous opioids, subsequently blocking opioid receptors in the PAG-RVM pathway (Sluka et al. 1999; Kalra et al. 2001). Reports of clinical effectiveness of TENS for phantom limb pain even when applied to the contralateral side (Katz et al. 1989; Giuffrida et al. 2010) support the second theory – the release of endogenous opioids by TENS.

Aversive stimulation and habituation When the intensity of stimulation increases to the extent that subjects feel pain, the stimulation becomes aversive or noxious. Ironically, repetitive painful stimulation leads to reduced pain, i.e., habituation (Bingel et al. 2007; Rennefeld et al. 2010). In a recent study (Rennefeld et al. 2010), daily painful thermal stimulation of the left volar forearm for 1 week was delivered to healthy subjects. Significant pain attenuation was observed at the site of stimulation, the contralateral arm and the ipsilateral leg. In the same study, the authors also found that pain habituation to noxious stimulation was unaffected by the opioid antagonist naloxone. Thus, these results strongly support a central mechanism of pain habituation that does not directly involve the endogenous opioid system. *The naloxone non-reversible effect by aversive electrical stimulation suggested that the effect was mediated by a mechanism different from the release of endogenous opioids*, as described for TENS and acupuncture. Brain imaging studies after painful thermal (Bingel et al. 2007) and electrical (Christmann et al. 2007) stimulation revealed that, in addition to decreased activity in classical pain areas, including thalamus, insula, putama and somatosensory cortices, pain-related responses in the ACC significantly decreased over time. The ACC has been reported to selectively process the aversive quality of noxious stimulation (LaGraize et al. 2006), but does not influence sensation of the stimulation (LaBuda and Fuchs 2005). The brain imaging findings of decreased pain-related responses in the ACC after repetitive aversive stimulation indicates a negative effect on the affective processing of the stimulation, subsequently resulting in less unpleasantness over time, without changes in sensation of noxious stimuli.

Acupuncture and electro-Acupuncture for pain

Acupuncture is a special kind of neurostimulation that is applied to acupuncture points (Acupoints). Acupoints are special points located in the periphery but are connected to internal organs including spinal cord and brain, following different channels, according to traditional Chinese medicine. Systematic investigation on mechanisms of acupuncture started in 1950s in China (Han 2004). Evidence on clinical effectiveness and mechanisms has accumulated over decades in Western Medicine literature (Hui et al. 2000; Han 2004; Yoo et al. 2004; Cho et al. 2006; Dhond et al. 2008). Acupuncture for pain relief via the release of endogenous opioids has been well accepted in Western Medicine. Modification to traditional acupuncture needle has been made (Han et al. 1981; Han 2004). It has been replaced by a surface electrode (or equivalent). When a specialized electrode is placed over traditional acupoints, electrical stimulation is delivered. This modification has been termed electroacupuncture. Needle acupuncture and electroacupuncture are both effective in analgesia (Wan et al. 2001; Huang et al. 2002). *The effect of electroacupuncture is usually reliable, but dependent on intensity and frequency of delivered electrical stimulation: different frequency of electrical stimulation generates different endogenous opioids, and the analgesic effect is naloxone-reversible* (Huang et al. 2002; Han 2004).

Aversive electrical stimulation to acupuncture points

Theoretically, analgesic effects are anticipated to be strengthened if different mechanisms of treatment are delivered at the same time. Following this line, repetitive aversive electrical stimulation delivered to acupoints is expected to have combined effects: 1) habituation to aversive stimulation as described above; 2) analgesic effect secondary to the release of endogenous opioids secondary to stimulation of acupuncture points. Therefore, *in combining different mechanisms (the release of endogenous opioids, habituation), aversive electrical stimulation to acupoints is theoretically anticipated to produce significant analgesic effects.*

Psychological/Cognitive coping /Cognitive behavioral therapy

In addition to the above modalities, a variety of approaches is available for managing psychological and environmental contributions to pain and distress. Pharmacological strategies such as anxiolytic and antidepressant therapy and non-pharmacological strategies such as cognitive behavioral approaches may be used. The use of cognitive-behavioral therapy, including mirror therapy (Barbin et al. 2016) and virtual reality therapy (Ortiz-Catalan et al. 2016) has been reported to modify phantom limb pain. These techniques may act by modifying the central process involved in pain perception.

• Human breathing and possible effects on modulation of pain

As briefly mentioned, respiration and pain are co-modulated at the sub-cortical level (The PAG) as part of vital surviving functions. Human breathing is a very unique motor act. It can be controlled reflexively (automatic breathing), e.g., during sleep, while humans are also able to breathe voluntarily when needed (voluntary breathing), e.g., singing, speech, etc. Automatic breathing is believed to originate in the brainstem via the ponto-medullary respiratory oscillator. A descending bulbo-spinal projection from the oscillator synapses with the spinal cord anterior horn cells with rhythmic projections to the respiratory muscles to cause automatic breathing. The oscillator can function automatically without any peripheral feedback, and only responds to changes in pH and P_{CO_2} . (cf. review (Guz 1997)). In contrast, cortical inputs are required during voluntary breathing. Spinal motoneurons receive cortico-spinal inputs originating from discrete regions of the motor cortex where the respiratory muscles are represented. These cortical areas are clearly identified in humans (Gandevia and Rothwell 1987; Colebatch et al. 1991; Maskill et al. 1991; Sharshar et al. 2004). Clinical evidence strongly suggests that bulbo-spinal fibers project separately from the relevant corticospinal fibers. For instance, patients with brainstem lesions (Plum and Leight 1981) or very high cervical cord lesions (Davis and Plum 1972; Lahuerta et al. 1992) can breathe voluntarily, but lack automatic breathing when drowsy or asleep. Cortico-spinal pathways could bypass the brainstem respiratory centers and provide direct cortical control to the spinal respiratory motoneurons during voluntary breathing (Corfield et al. 1998). During normal functioning, spinal motoneurons are able to integrate these different sources, including descending cortico- and bulbo-spinal inputs and peripheral afferent inputs into a segmental interneuronal network (Aminoff and Sears 1971).

During voluntary breathing, humans need to voluntarily suppress autonomic control of breathing (Guz 1997; Haouzi et al. 2006) through voluntary cortical activation (the “cortical respiratory center”). Brain imaging studies (Colebatch et al. 1991; Maskill et al. 1991; Ramsay et al. 1993; Fink et al. 1995; Evans et al. 1999; Smejkal et al. 1999; Smejkal et al. 2000; Macey et al. 2003; Macey et al. 2004; Mazzone et al. 2007; Evans et al. 2009; Evans 2010) have demonstrated extensive involvement of

cortical areas bilaterally, including the primary motor cortex (M1), the premotor cortex, the supplementary motor area, the primary and secondary somatosensory cortices, the insula, the ACC and amygdala, and the dorsolateral prefrontal cortex. The insula is known to have strong connections to brainstem centers (Tsumori et al. 2006). Respiratory specific insular connections include the medullary respiratory chemoreceptors and pulmonary stretch receptors (Gaytan and Pasaro 1998; Hanamori et al. 1998). *Activity of the insular cortex is not modulated during automatic breathing, according to breath-by-breath analysis in a recent fMRI study (Evans et al. 2009). The insula and associated operculum, however, are consistently activated during various sensorimotor respiratory tasks (Evans 2010). Change in respiratory status, e.g., urge-to-cough (Mazzone et al. 2007), needs a change in pulmonary stretch receptor or chemoreceptors (Gaytan and Pasaro 1998; Hanamori et al. 1998), leading to increased activity in the insula, thus possibly to provide respiratory interoception (Craig 2002).*

[figure not shown]
- **Breathing-controlled electrical stimulation (BreESTim) for pain management – Preliminary data**

